10.1.3. Population of Interest

The pharmacokinetic analyses will be based on the PK population, unless otherwise specified.

10.1.4. Strategy for Intercurrent (Post-Randomization) Events

Any intercurrent events are taken to be irrelevant for pharmacokinetic endpoints. The pharmacokinetic endpoints will be summarized based on available and observed data.

11. POPULATION PHARMACOKINETIC (POPPK) ANALYSES

No population pharmacokinetics analyses are planned for this study, but the pharmacokinetic data may be used for a separate report.

12. PHARMACODYNAMIC ANALYSES

No pharmacodynamics analyses are planned for this study, but the pharmacodynamic data may be used for a separate report.

13. PHARMACOKINETIC / PHARMACODYNAMIC ANALYSES

No pharmacokinetic / pharmacodynamic analyses are planned for this study, but the pharmacokinetic / pharmacodynamic data may be used for a separate report.

15. APPENDICES

15.1. Appendix 1: Protocol Deviation Management and Definitions for Per Protocol Population

15.1.1. Exclusions from Per Protocol Population

A subject meeting any of the following criteria will be excluded from the Per Protocol population:

Number	Exclusion Description
01	Informed Consent in Deviation Category
02	Eligibility Criteria Not Met in Deviation Category
03	Not Withdrawn After Developing Withdrawal Criteria in Deviation Category
04	Wrong study treatment or assignment administered in Deviation Subcategory
05	Randomization procedures (e.g. subject assigned to wrong stratum or subject randomized out of order) in Deviation Subcategory
06	Less than 3 out of 4 scheduled evaluable Hgb values from the primary efficacy evaluation period ¹
07	Subject received prohibited medication for more than 14 days during study period ²
08	Non-compliance with randomized medication (compliance category of under compliant or over compliant) ³ during the primary efficacy evaluation period, based on eCRF randomized medication exposure and compliance forms

NOTES:

[1] Evaluable Hgb values are described in Section 15.6.3.

[2] Prohibited medications include strong inhibitors of CYP2C8 (e.g. gemfibrozil) and strong inducers of CYP2C8 (e.g. rifampin/rifampicin), not include erythropoietin (e.g., epoetin/ darbepoetin alfa/ epoetin beta pegol, excluding epoetin beta pegol supplied by GSK).

[3] See Section 15.6.2; Under compliant: <80%, compliant ≥80% and ≤120%, over compliant >120%

CONFIDENTIAL

201753

15.2. Appendix 2: Schedule of Activities
15.2.1. Protocol Defined Schedule of Events

Phase	Screening ⁹	Treatment															Follow-up	
Week	-4	Day 1	2 ¹⁰	4	8	12	16	20	24	28	32	36	40	44	48	52	Early withdrawal ¹⁰	4 weeks after 52 or withdrawal
Permissible range (days)	±7	-	±3	±3	±5	±5	±5	±5	±5	±5	±5	±5	±5	±5	±5	±5	-	±7
Informed consent	X																	
Inclusion/exclusion criteria	X	X																
Medical history, demography, height, weight	X																	
IWRS call	X	X	X	X	X	X	X	X	X	X	X	X	X	X	X	X	X	X
Study medication dispensing ^{1,2}		X	X ¹⁰	X	X	X	X	X	X	X	X	X	X	X	X			
Study treatment compliance			X ¹⁰	X	X	X	X	X	X	X	X	X	X	X	X	X	X	
Vital signs	X	X		X			X			X			X			X	X	X
Ophthalmology ³	↔					↔										↔		
ECG	X								X							X		
HemoCue Hgb	X	X	X	X	X	X	X	X	X	X	X	X	X	X	X	X		
Hematology	X	X	Only Hgb	X	Only Hgb	Only Hgb	X	Only Hgb	Only Hgb	X	Only Hgb	Only Hgb	X	Only Hgb	Only Hgb	X	X	X
Clinical chemistry	X	X		X			X			X			X			X	X	X
Urinalysis (ND subjects only)	X	X							X							X		X
Pregnancy test (urine or serum hCG) ⁴	X	X		X			X			X			X			X	X	X
Estradiol, FSH ⁵	X																	
PK ⁶						X			X									
Ferritin, TSAT	X	X		X			X			X			X			X	X	
Serum iron, TIBC, UIBC, serum transferrin, hepcidin		X		X			X			X			X			X	X	
iPTH		X								X						X		
HR-QoL		X				X				X						X	X	
Genetics sample ⁷		X																

15.3. Appendix 3: Assessment Windows

All data will be reported according to the nominal visit date for which it was reported (that is, no visit windows will be applied during dataset creation). Permissible range at each visit was specified in time & event table (See [Appendix 2](#)). Records in the eCRF unscheduled visit will not be slotted to a particular time point, but remain as unscheduled if they are either summarized or listed unless otherwise specified.

15.3.1. Definitions of Assessment Windows for Analyses

Analysis Time Point	Definitions
Screening ^[1]	Data collected in Screening visit If multiple records are present, the latest record will be used for analysis.
Day 1 ^[1]	Data collected in Day 1 visit If multiple records are present, the latest record will be used for analysis.
Week 2	Data collected in Week 2 visit ^[2]
Week 4	Data collected in Week 4 visit
Week 8	Data collected in Week 8 visit
Week 12	Data collected in Week 12 visit
Week 16	Data collected in Week 16 visit
Week 20	Data collected in Week 20 visit
Week 24	Data collected in Week 24 visit
Week 28	Data collected in Week 28 visit
Week 32	Data collected in Week 32 visit
Week 36	Data collected in Week 36 visit
Week 40	Data collected in Week 40 visit
Week 44	Data collected in Week 44 visit
Week 48	Data collected in Week 48 visit
Week 52	Data collected in Week 52 visit
Follow-up	Data collected in Follow-up visit

Note:

Any unscheduled visit will not be slotted to a particular time point.

[1] For rescreened subjects, data collected in screening-pass visit (i.e. screening and day 1 visit where the subject has passed a screening test) will be used for analysis. They may have multiple records at Screening and/or Day 1 visit, which associates with a screening pass visit and screening failure visit(s) (see Section [15.6.1](#) and Section [15.6.2](#))

[2] Only ND subjects randomized to Cohort 3

15.4. Appendix 4: Study Phases and Treatment Emergent Adverse Events

15.4.1. Study Phases

Assessments and events will be classified according to the time of occurrence relative to randomization date and treatment stop date.

Treatment Stop Date is defined in Section 15.6.1.

15.4.1.1. Study Phases for Hgb Data

Treatment State	Definition
Pre-therapy	Date \leq Randomization Date
On-therapy	Randomization Date $<$ Date \leq Treatment Stop Date + 1 day
Post-therapy	Date $>$ Treatment Stop Date + 1 day

NOTES:

- If randomization date is missing then the assessment will be considered to be pre-therapy

15.4.1.2. Study Phases for AE Data

On therapy AEs will be treated as treatment emergent AEs, therefore, treatment emergent flag for AEs will be derived from on-therapy treatment state.

Treatment State	Definition
Pre-therapy	AE Start Date $<$ Randomization Date
On-therapy	Randomization Date \leq AE Start Date \leq Treatment Stop Date + 1 day
Post-therapy	AE Start Date $>$ Treatment Stop Date + 1 day
Duration (Days)	AE Resolution Date – AE Onset Date + 1 day
Drug-related	If relationship is marked 'YES' on eCRF or value is missing.

NOTES:

- If randomization date is missing then the assessment will be considered to be pre-therapy

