8.2.1. Planned Adverse Events of Special Interest Analyses Displays

- **AEs of Special Interest (AESIs)**

AEs of Special Interest

The number and percentage of subjects reporting at least one AESI will be provided by treatment group. These events will be summarized by each AESI term (See Section [15.6.4](#)). On-therapy and post-therapy AESIs will be summarized separately.

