15.6. Appendix 6: Derived and Transformed Data

15.6.1. General

Multiple Measurements at One Analysis Time Point

 Subjects having both High and Low values for Normal Ranges at any post-baseline visit for safety parameters will be counted in both the High and Low categories of “Any visit post-baseline” row of related summary tables. This will also be applicable to relevant PCI summary tables. For multiple measurements at Screening and/or Day 1 visit, the screening pass visit record will be used for analysis (See Appendix 3: Assessment Windows)
Study Day

 Calculated as the number of days from Randomization Date: 
 Ref Date = Missing → Study Day = Missing Ref Date < Randomization Date → Study Day = Ref Date - Randomization Date Ref Date ≥ Randomization Date → Study Day = Ref Date - (Randomization Date) + 1
Unique Subject ID

 All subjects have unique subject ID for analyses even if a subject was enrolled after rescreened. Tables/figures/listings will be produced based on unique subject ID. For a rescreened subject, the unique subject ID will be derived from the first-assigned subject number though he or she seems to have different subject numbers in eCRF by screening assessments.
Rescreening Subjects

 For rescreened subjects, data collected in screening-pass visit will be used for analysis. They may have multiple records at Screening and/or Day 1 visit, which associates with a screening-pass visit and screening failure visit(s) Regarding a listing of SAEs in screening period, all pre-therapy SAEs captured in eCRF will be provided including screen failure records of rescreened subjects.
Treatment Start Date

 First randomized treatment start date
Treatment Stop Date - Daprodustat

 Calculated as the latest treatment stop date.
Treatment Stop Date – Epoetin Beta Pegol

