
 Following definition will be based on “assumed” treatment stop date because the treatment stop date is not captured in eCRF. 
Definition:
 
 If a subject has completed the treatment period (i.e., Week 52 visit record is present), treatment stop date will be calculated as Week 52 visit date.. 
 Week 52 visit date will be based on laboratory Hgb date. HemoCue Hgb date will be used when laboratory Hgb date is unavailable. If a subject has withdrawn from the treatment period (i.e., Week 52 visit record is missing), treatment stop date will be calculated as the latest dosing start date + XX days (1 day before the next treatment start date if a subject hadn’t withdrawn) 
 Subjects will have every 2 weeks or every 4 weeks injection of epoetin beta pegol, therefore assumed treatment stop date could include “+ 13 or 27 days” to mimic every 2 weeks or every 4 weeks dosing.

Subgroup definition
 
 For general considerations, see Section 5.4.2 Regarding prior ESA type, prior ESA dose, and ERI, see Section 15.6.2 Baseline iron use = use or non-use of pre-therapy iron medications (including ferric citrate (trade name Riona), see Section 15.6.3). History of diabetes will be derived from the current history diabetes (Yes/No) in medical history records. CKD stage will be derived from the eGFR measurement at a screening visit Cohort will be derived from the randomization number. 
 Cohort 1 = Randomization Number in PPD Cohort 2 = Randomization Number in PPD Cohort 3 = Randomization Number in PPD Dialysis will be derived from the randomization number. 
 ND subjects = Cohort 1 or 3 PD subjects = Cohort 2

Time Definitions (per GSK standard principles)
 
 1 week = 7 days 1 month = 30.4375 days 1 year = 365.25 days

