15.6.4. Safety

Adverse Events
AE up to Week 4

 • Cut-off date of Week 4 for individuals will be based on Week 4 visit date which is associated with the earliest date throughout Week 4 records (i.e., SDTM.SVSTDTC).
AEs of Special Interest (AESIs)

AESIs are manually-selected at patient-level (i.e. following case-by-case review by members of the SRT including representatives from the local Japan team) and not at preferred term level.
 
AESI categories are classified as follows:
 
 • Thrombosis and/or tissue ischemia secondary to excessive erythropoiesis • Death, myocardial infarction, stroke, heart failure, thromboembolic events, thrombosis of vascular access • Cardiomyopathy • Pulmonary artery hypertension • Cancer-related mortality and tumor progression and recurrence • Esophageal and gastric erosions • Proliferative retinopathy, macular edema, choroidal neovascularization • Exacerbation of rheumatoid arthritis 
Following events will be programmatically identified as AESIs.
 
Thrombosis and tissue ischemia events will be considered to be secondary to excessive erythropoiesis if during the window of [AE start date – 30 days, AE start date +15 days] any one of the following 3 events occurs:
 
 • Any Hgb value > 13 g/dL • Hgb increase > 2 g/dL over 2 weeks (applied to only Cohort 3) • Hgb increase > 4 g/dL over 4 weeks 
Note: Thrombosis and tissue ischemia events that need to be considered against the above 3 Hgb events will be identified by the case-by-case review.
 
Note: HemoCue and central laboratory values will be considered separately. Unscheduled Hgb values will also be used in the assessment of secondary to excessive erythropoiesis if available.
 
Note: All Hgb values that have an assessment date within the window of [AE start date – 58 days, AE start date + 15 days] will be considered.
 
Any SAE which outcome is fatal will be identified AESI as death.

CV Events

Patient profiles of CV events will be provided according to records captured in eCRF, except for Peripheral Arterial Thrombosis Embolism (PAT) form.
 
CV events in PAT form will be provided only when a related AE sequence number is not present. This is because several records in PAT form are captured just for AESI information instead of CV events.

Laboratory Parameters

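### After a mid-interval withdrawal, the on-therapy AE window runs longer for epoetin than for daprodustat, tilting the on-therapy AE, SAE and AESI comparison modestly against epoetin

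*SAP*

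**What the plan says.** Section 15.4.1.2 counts an AE as on-therapy if it starts between randomization and "Treatment Stop Date + 1 day". The same section makes this the treatment-emergent definition: "On therapy AEs will be treated as treatment emergent AEs, therefore, treatment emergent flag for AEs will be derived from on-therapy treatment state". Section 15.4.1 sends the reader elsewhere for the key date: "Treatment Stop Date is defined in Section 15.6.1".

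Section 15.6.1 then defines that date separately for each arm.

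- Daprodustat: "Calculated as the latest treatment stop date", read here as the recorded date of the last tablet.
- Epoetin beta pegol, completers: the date of the Week 52 visit.
- Epoetin beta pegol, withdrawals: the eCRF captures no stop date, so one is assumed. The rule is that "treatment stop date will be calculated as the latest dosing start date + XX days", with 13 or 27 days added "to mimic every 2 weeks or every 4 weeks dosing". In effect this is the day before the next injection would have been given.

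Sections 8.1.1 and 8.2.1 present SAEs and AESIs as numbers and percentages of subjects, with the phases kept apart. For AESIs: "On-therapy and post-therapy AESIs will be summarized separately". In the headline deliverable (15.10.3), the ND tables for AEs, SAEs and AESIs (3.1, 3.55 and 3.65) are all on-therapy. The post-therapy counterparts are Tables 3.23, 3.57 and 3.67. The safety table list in 15.10.4.4 contains no AE, SAE or AESI table that joins the two phases.

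**The concern.** The two stop dates do not mark the same moment. The daprodustat date follows the decision to stop. The epoetin date follows the injection calendar and takes no account of when the decision was made. An SAE that starts a few days after a mid-interval decision to stop can therefore be treatment-emergent in one arm and post-therapy in the other.

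The trial is open-label, with about 286 ND subjects randomized 1:1. SAEs and AESIs may be few, so moving one or two subjects between tables can change how the safety comparison reads. The events at risk of being moved are those close to discontinuation.

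**Working it through.** **1. Reproduce the offsets.** Offset = dosing interval − 1: 14 − 1 = 13 and 28 − 1 = 27, as in Section 15.6.1. Adding the one-day allowance, the on-therapy state ends 14 or 28 days after the last injection in an epoetin withdrawal, and 0 + 1 = 1 day after the last tablet for daprodustat.

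**2. Find the part that differs between arms.** Let the decision to stop fall u days after an injection. The daprodustat window closes at u + 1 and the epoetin window at 28 (or 14). The excess is 28 − (u + 1) = 27 − u days on 4-weekly dosing and 13 − u on 2-weekly dosing.

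- 4-weekly: 0 to 27 days, mean 13.5 if u is uniform over 0 to 27.
- 2-weekly: 0 to 13 days, mean 6.5 if u is uniform over 0 to 13.
- About 0 if the subject stops when the next injection is due.
- Completers in both arms close at about Week 52 plus one day, so they contribute no difference.

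**3. Example.** An SAE starting 5 days after the decision is always post-therapy for daprodustat. On 4-weekly epoetin it is on-therapy if u + 5 ≤ 28, which is 24 of 28 equally likely days (86%). On 2-weekly dosing it is on-therapy if u + 5 ≤ 14, which is 10 of 14 (71%).

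**4. Extra person-time (assumed rates).** The SAP gives neither withdrawal nor event rates. Take 286/2 = 143 subjects in the epoetin arm, 10% to 30% withdrawal and a mean excess of 13.5 days:

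- 143 × 0.10 × 13.5/365.25 = 0.53 person-years; with 0.30 it is 1.59. This is about 0.4% to 1.3% of the arm's exposure.
- Extra subjects with an SAE = 143 × w × (1 − exp(−r × 13.5/365.25)), with w the withdrawal proportion and r the yearly SAE rate. This gives 0.2 to 0.5 subjects at r = 0.3, 0.5 to 1.6 at r = 1, and 1.5 to 4.5 at r = 3.

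**5. Simulation with equal true hazard in both arms.** There were 1,000,000 simulated subjects per scenario. Assumptions: SAE rate 0.3 per year; 30% of SAEs cause stopping; other stops at a constant hazard that would give 10%, 20% or 30% by day 364; hazard after such a stop multiplied by 1, 5 or 10; 4-weekly injections. Percentage with an on-therapy SAE under the SAP rule, daprodustat / epoetin (difference):

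| Other stops | ×1 | ×5 | ×10 |
|---|---|---|---|
| 10% | 24.65 / 24.74 (+0.09) | 24.65 / 25.11 (+0.46) | 24.70 / 25.56 (+0.86) |
| 20% | 23.37 / 23.56 (+0.19) | 23.43 / 24.33 (+0.90) | 23.52 / 25.23 (+1.71) |
| 30% | 21.93 / 22.21 (+0.28) | 22.02 / 23.38 (+1.36) | 22.21 / 24.80 (+2.59) |

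**6. Would one day after the last injection be fairer?** No. With multiplier 1, epoetin would show 17.46% against 24.65% (10% other stops) and 15.42% against 21.93% (30%). That is a tilt of 7.19 and 6.51 points in the opposite direction.

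**7. Post-therapy tables.** The schedule in Section 15.2.1 places follow-up 4 weeks after Week 52 or withdrawal in both arms. For a 4-weekly epoetin withdrawal, on average about 13.5 of those 28 days, roughly half, still count as on-therapy. The post-therapy tables therefore carry the reverse tilt.

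**The case against.** The strongest defence is that the epoetin rule is deliberate and mostly right. Each window runs one dosing interval past the last dose. Much of the 28 days corresponds to time when a daprodustat subject is still swallowing tablets, and an event that itself causes stopping can fall anywhere in the injection interval. Step 6 shows that the interval-based rule removes a much larger bias. This stands. A reader might infer that the whole gap of 1 versus 28 days is bias; the documents do not support that, and only the remainder of the interval after the decision is at issue.

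A reader might also see a contradiction with Section 15.6.4, which says "Thrombosis and tissue ischemia events will be considered to be secondary to excessive erythropoiesis if during the window of" 30 days before to 15 days after AE onset one of three Hgb conditions occurs. That would suggest the plan recognises a 30-day drug-risk period which the one-day allowance ignores. It does not. The rule uses Hgb measured after the event as well as before it, classifies the event's mechanism rather than exposure, and is not limited to on-therapy events. Nothing there conflicts with 15.4.1.2.

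Nor is the information lost. Post-therapy tables exist, and the listings of all AEs, fatal and non-fatal SAEs, AESIs and exposure (Listings 36, 39, 40, 44, 13 and 14) would allow events to be reclassified. But that means rebuilding the comparison by hand. Adding the on-therapy and post-therapy tables is not valid, because a subject can appear in both.

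**Conclusion.** The concern holds in a limited form. For mid-interval withdrawals, the SAP keeps epoetin subjects on-therapy for 0 to 27 days longer after the decision to stop than daprodustat subjects. The on-therapy AE, SAE and AESI comparison in ND subjects is tilted modestly against epoetin, with the reverse tilt post-therapy, and no planned summary table removes either.

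The direction follows from the SAP's definitions. The size does not: the means of 13.5 and 6.5 days assume uniform timing of the decision, and the 0.1 to 2.6 percentage points rest on assumed withdrawal and SAE rates. The upper values need a five- to tenfold rise in hazard after stopping. With no such rise the tilt is 0.1 to 0.3 points. The existing tables need a supplement; they do not need replacing.

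**What to change.** In Section 15.4.1.2, add one flag, identical in both arms and independent of Treatment Stop Date, for AEs starting from the randomization date to the follow-up visit (4 weeks after Week 52 or withdrawal). In Section 15.10.4, add ND tables of AEs, SAEs and AESIs on that flag and present them beside the current on-therapy and post-therapy tables.

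A window counted from the last dose, such as last dose plus 28 days in both arms, should not be used instead. Daprodustat would get 28 days after the decision and 4-weekly epoetin only 28 − u, about 14 on average, which reverses the tilt. Capping the assumed epoetin date at death would not help either, since no AE starts after death.

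The cost is one derived flag and three or four tables from data already collected. The common window includes some off-drug days, which is a reason to keep the existing tables alongside.

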15.4.1.3. Study Phases for Concomitant Medication

Treatment State	Definition
Pre-therapy	Concomitant medications that meet either following conditions will be regarded as pre-therapy. 
 • Concomitant Medication Start Date $<$ Randomization Date [a, b, c, j, n] • Concomitant Medication Start Date is missing [g, h, i, m, o] • Randomization Date is missing
On-therapy	Concomitant medications that meet either following conditions will be regarded as on-therapy. 
 • Randomization Date \leq Concomitant Medication Start Date \leq Treatment Stop Date + 1 [d, e, k, p, q, r, s, v] • (Concomitant Medication Start Date $<$ Randomization Date) AND (Randomization Date \leq Concomitant Medication Stop Date) [b, c, n]

Treatment State	Definition
	
 • (Concomitant Medication Start Date < Randomization Date) AND (Concomitant Medication Stop Date is missing) [j] • (Concomitant Medication Start Date is missing) AND (Concomitant Medication Stop Date ≥ Randomization Date) [h, i, o] • (Concomitant Medication Start Date is missing) AND (Concomitant Medication Stop Date is missing) [m]
Post-therapy	
Concomitant medications that meet either following conditions will be regarded as post-therapy.
 
 • Concomitant Medication Stop Date > Treatment Stop Date [c, e, f, l, r, t, v] • Concomitant Medication Stop Date is missing [j, k, l, m, s, u]

NOTES:

- Data of concomitant medication includes anti-hypertensive medication, ESA, iron, and blood products and blood supportive care products.
- Alphabets in brackets after the conditions correspond to each case in following illustrations.

Illustrations of the pre-therapy, on-therapy, and post-therapy for concomitant medications are included below:

	Pre-therapy	On-therapy		Post-therapy		Pre-therapy medication	On-therapy medication	Post-therapy medication
(a)	x—x					Y	N	N
(b)	x—		—x			Y	Y	N
(c)	x—		—			Y	Y	Y
(d)			x—x			N	Y	N
(e)			x—			N	Y	Y
(f)						N	N	Y
(g)	?—x					Y	N	N
(h)	?—		—x			Y*	Y	N
(i)	?—		—			Y*	Y*	Y
(j)	x—		—			Y	Y**	Y**
(k)			x—			N	Y	Y**
(l)						N	N	Y
(m)	?—		—			Y***	Y***	Y***
(n)	x—	x				Y	Y	N
(o)	?—	x				Y*	Y	N
(p)		x	—x			N	Y	N
(q)		x	—			N	Y	N
(r)				x		N	Y	Y
(s)				x		N	Y	Y**
(t)					x	N	N	Y
(u)					x	N	N	Y
(v)			x—		x	N	Y	Y

x = start/stop date of medication
 ? = missing start/stop date of medication
 * If a medication is stopped on-therapy or post-therapy and no start date is recorded it will be assumed that the medication was ongoing from the pre-therapy phase
 ** If a medication is started pre-therapy or on-therapy and no stop date is recorded then usage will be assumed to be ongoing for the remainder of the study
 *** If a medication has no start or stop date it will be assumed that the medication was ongoing from the pre-therapy phase to the post-therapy phase

